24.9 Dose Modification

[Table 30](#) provides dose reductions options for acalabrutinib.

Table 30 Acalabrutinib Dose Reduction Options

Starting dose	1 st dose reduction ^a	2 nd dose reduction
100 mg twice daily	100 mg once daily	Discontinue

^a When reducing to 100 mg acalabrutinib once daily, the morning dose should be retained. If considering dose reduction, please discuss with the Medical Monitor.

Note: Temporary withholding of acalabrutinib for as little as 7 days can cause a transient worsening of disease in MCL and/or of constitutional symptoms. Transient worsening of disease during temporary interruption of acalabrutinib (eg, for drug-related toxicity, surgery, or intercurrent illness) may not indicate disease progression. In such circumstances, and if medically appropriate, following discussion with the Medical Monitor, participants may resume therapy and relevant clinical, laboratory, and/or radiologic assessments should be done to document whether tumour control can be maintained or whether actual disease progression has occurred.

If the dose of acalabrutinib is reduced for apparent treatment-related AE/SAE, the dose of acalabrutinib should not be re-escalated unless the participant tolerates the reduced dose for greater than 4 weeks and at the Investigator's discretion and in consultation with the Medical Monitor. Such re-escalation may be particularly warranted if further evaluation reveals that the AE/SAE that led to the dose reduction was not treatment-related. Any changes to the dosing regimen must be recorded on the appropriate eCRF.

Acalabrutinib dose reduction options are described in and dose modification and discontinuation guidelines for haematological and non-haematological toxicities (excluding abnormal liver chemistry results) are shown below in [Table 30](#). Dose modifications for AZD4573 and acalabrutinib for abnormal liver chemistry results are described in [Table 31](#).

In general, if a participant experiences a Grade 1 or Grade 2 haematological or non-haematological toxicity, no dose modification is required. If a participant experiences a Grade 3 or Grade 4 toxicity, not attributable to the disease or disease-related processes under investigation, dosing will be interrupted and/or the dose reduced (see [Table 30](#) for acalabrutinib reduction options and [Table 31](#) for recommended dose modifications for AZD4573 and acalabrutinib) and supportive therapy administered as required. If the toxicity resolves or reverts to CTCAE Grade ≤ 2 within 21 days and the participant was showing clinical benefit, treatment with study treatment(s) may be restarted.

If the toxicity does not resolve to CTCAE Grade ≤ 2 within 21 days, then the participant should be withdrawn from the study and observed until resolution of the toxicity. Maximal drug interruption allowed for related toxicity for both AZD4573 and acalabrutinib is ≤ 21 consecutive days.

Table 31 Recommended Dose Modifications for AZD4573 and Acalabrutinib

Event ^a	Occurrence	Action with AZD4573	Action with Acalabrutinib
Tumour Lysis Syndrome (TLS) – Howard Modification of Cairo-Bishop Criteria			
Changes in uric acid, potassium, phosphorus, creatinine or calcium, or symptoms suggestive of clinically significant TLS, in the Investigator's judgement	Any	For any abnormal changes present before dosing, initiate supportive therapy and hold drug for up to 7 days. If not resolved, reduce by 1 dose level.	Withhold acalabrutinib until resolved, resume dosing at the same dose level upon resolution.
		For events of Grade 1 or 2 TLS, resume at same dose level upon resolution.	For events of Grade 1 or 2 TLS, resume at same dose level upon resolution.
	For 1st occurrence of Grade 3 TLS resume at the same dose upon resolution to Grade 1.	For 1st occurrence of Grade 3 TLS resume at the same dose upon resolution.	
	For 2nd occurrence of Grade 3 TLS, after resolution to Grade 1, reduce dose by one dose level when restarting AZD4573 except events that in the opinion of the Investigator, in consultation with the Medical Monitor, are not dose-limiting.	For 2nd occurrence of Grade 3 TLS, after resolution to Grade 1, reduce dose by one dose level when restarting or discontinue acalabrutinib except events that in the opinion of the Investigator, in consultation with the Medical Monitor, are not dose-limiting.	
	For subsequent occurrences of Grade 3 TLS, further rechallenge and dose level to be discussed with the Medical Monitor.	For subsequent occurrences of Grade 3 TLS, further rechallenge and dose level to be discussed with the Medical Monitor.	
	For events of Grade 4 TLS, discontinue AZD4573.	For events of Grade 4 TLS, discontinue acalabrutinib.	

Table 31 Recommended Dose Modifications for AZD4573 and Acalabrutinib

Event ^a	Occurrence	Action with AZD4573	Action with Acalabrutinib
Non-haematological Toxicities (Except Liver Dysfunction)			
Grade 3 or 4 non-haematological toxicities	1 st occurrence	
Withhold dosing with AZD4573 until the toxicity has resolved to Grade 1, but no longer than 21 days^b.
 
Adequate supportive therapy as per institutional guidelines should be given. AZD4573 therapy may be resumed at the same dose. No dose modification is required.
	
Withhold acalabrutinib until recovery to Grade ≤ 2.
 
Restart acalabrutinib at the same dose level.

	2 nd and subsequent occurrences	
Withhold dosing AZD4573 up to 21 days^b.
 
Adequate supportive therapy as per institutional guidelines should be given.
 
After resolution to Grade 1, reduce dose by one dose level when restarting AZD4573.
 
If no resolution within 21 days discontinue AZD4573^b.
 
In case of subsequent occurrences, dosing may be modified to skip weekly dose(s) (eg, 2 weeks on/1 week off or to 1 week on/1 to 2 weeks off), after discussing with the Medical Monitor.
	
Withhold acalabrutinib until recovery to Grade ≤ 2.
 
Restart acalabrutinib with 1 level dose reduction or discontinue (see Table 30).

Table 31 Recommended Dose Modifications for AZD4573 and Acalabrutinib

Event ^a	Occurrence	Action with AZD4573	Action with Acalabrutinib
Haematological Toxicities			
Grade 3 or 4 neutropenia without fever or infection, lasting > 7 days despite growth factor support	1 st occurrence	Withhold dosing AZD4573 until Grade ≤ 2 or baseline level. Restart at same dose level following resolution.	Withhold acalabrutinib if Grade 4 neutropenia lasting > 7 days until resolution to Grade ≤ 2 or baseline level and then restart at same dose for 1st occurrence .
	2 nd and subsequent occurrence	Withhold dosing AZD4573 until Grade ≤ 2 or baseline level. Restart with one dose level reduction following resolution. In case of subsequent occurrences , dosing may be modified to skip weekly dose(s) (eg, 2 weeks on/1 week off or to 1 week on/1 to 2 weeks off), after discussing with the Medical Monitor.	Withhold acalabrutinib if Grade 4 neutropenia lasting > 7 days until resolution to Grade ≤ 2 or baseline level and then restart at a reduced dose or discontinue (see Table 30).
Grade 3 or 4 neutropenia with infection or fever	1 st occurrence	Withhold dosing AZD4573. To reduce the infection risks associated with neutropenia, G-CSF may be administered with AZD4573 if clinically indicated/required as per Institutional practice. Consider secondary prophylaxis with G-CSF as per ASCO/ESMO guidelines. Once the toxicity has resolved to ≤ Grade 2 or to baseline level, AZD4573 therapy may be resumed at the same dose.	Withhold acalabrutinib until infection is resolved, antibiotics no longer required and ANC Grade ≤ 2 or baseline level. Following resolution, resume acalabrutinib with 1 level dose reduction or discontinue (see Table 30).

Table 31 Recommended Dose Modifications for AZD4573 and Acalabrutinib

Event ^a	Occurrence	Action with AZD4573	Action with Acalabrutinib
	2 nd occurrence	Withhold dosing AZD4573. Consider using G-CSF as clinically indicated/as per Institutional practice. Follow dose reduction guidelines when resuming treatment with AZD4573 after resolution. Reduce dose by one dose level.	Withhold acalabrutinib until infection is resolved, antibiotics no longer required and ANC Grade \leq 2 or baseline level. Following resolution, resume acalabrutinib with 1 level dose reduction or discontinue (see Table 30).
	3 rd occurrence	Discontinue AZD4573.	Discontinue acalabrutinib.
Grade 3 thrombocytopenia without bleeding	Any	Withhold AZD4573 until Grade \leq 2 or baseline level. Restart AZD4573 at the same dose level. Continued dosing can be considered at the discretion of the investigator after discussion with the medical monitor.	No action.
Grade 4 thrombocytopenia without bleeding requiring blood or platelet transfusion	1 st occurrence	Withhold AZD4573 until Grade \leq 2 or baseline level. Restart AZD4573 at the same dose level.	Withhold acalabrutinib until Grade \leq 2 or baseline level. Restart acalabrutinib at the same dose level.
	2 nd occurrence	Withhold AZD4573 until Grade \leq 2 or baseline level. Restart AZD4573 with 1 level dose reduction. If not recovered to Grade \leq 2 or baseline level discontinue.	Withhold acalabrutinib until Grade \leq 2 or baseline level. Restart acalabrutinib with 1 level dose reduction or discontinue (see Table 30).
	3 rd occurrence	Discontinue AZD4573.	Discontinue acalabrutinib.
Grade 3 or 4 thrombocytopenia with bleeding requiring blood or platelet transfusion	1 st occurrence	Withhold AZD4573 until Grade \leq 2 or baseline level. Restart AZD4573 with 1 level dose reduction. If not recovered to Grade \leq 2 or baseline level discontinue.	Withhold acalabrutinib until Grade \leq 2 or baseline level. Restart acalabrutinib with 1 level dose reduction or discontinue (see Table 30).

Table 31 Recommended Dose Modifications for AZD4573 and Acalabrutinib

Event ^a	Occurrence	Action with AZD4573	Action with Acalabrutinib
	2 nd occurrence	Discontinue AZD4573.	Discontinue acalabrutinib.

^a Adverse reactions are graded using National Cancer Institute CTCAE version 5.0. All grades refer to CTCAE grading except for TLS, which uses the Howard modification of Cairo-Bishop criteria (Howard et al 2011).

^b In cases where more than 21 days are needed, a decision to continue, modify, or discontinue study treatment will be made on a case-by-case basis in consultation with the principal Investigator and the Medical Monitor.

Abbreviations: ANC = absolute neutrophil count; ASCO = American Society of Clinical Oncology; CTCAE = Common Terminology Criteria for Adverse Events; ESMO = European Society for Medical Oncology; G-CSF = granulocyte-colony-stimulating factor; TLS = tumour lysis syndrome.

Dose modifications for AZD4573 and acalabrutinib for abnormal liver chemistry results are described in [Table 32](#).

Table 32 Recommended Dose Modifications for AZD4573 and Acalabrutinib for Abnormal Liver Chemistry Results

Event ^a	Action	
	AZD4573	Acalabrutinib
Isolated^b Elevations in ALT, AST, or Bilirubin		
Grade 1 Isolated ALT/AST $\leq 3 \times$ ULN or Isolated Bilirubin $\leq 1.5 \times$ ULN	Maintain current dose level. Monitor ALT, AST, ALP, and bilirubin at least 1x per week.	Maintain current dose level and schedule. Monitor ALT, AST, ALP, and bilirubin at least 1x per week.
Grade 2 Isolated ALT/AST > 3 to $\leq 5 \times$ ULN or Isolated Bilirubin > 1.5 to $\leq 3 \times$ ULN	After 7 days if hepatic enzymes resolve to Grade ≤ 1 , rechallenge at same dose level.	Withhold or continue acalabrutinib (at Investigator discretion, after discussion with the Medical Monitor). To prevent disease progression, monitor disease parameters closely. Monitor ALT, AST, ALP, and bilirubin at least 1x per week. After 7 days if hepatic enzymes appear to be improving and acalabrutinib was withheld, restart acalabrutinib at current dose level.

Event ^a	Action	
	AZD4573	Acalabrutinib
Grade 3 Isolated ALT/AST > 5-20 × ULN	If recovered to Grade ≤ 1 within 7 days, allow rechallenge at same dose level. If not recovered to baseline level within 7 days, discontinue AZD4573.	Withhold or continue acalabrutinib (at Investigator discretion, after discussion with the Medical Monitor). To prevent disease progression, monitor disease parameters closely.
Grade 3 Isolated Bilirubin > 3-10 × ULN	If recovered to baseline level within 96 hours (-2/+12 hours) of the start of the infusion allow rechallenge at same dose level. If not, discontinue AZD4573	Monitor ALT, AST, ALP, and bilirubin at least 1x per week. After 7 days if hepatic enzymes appear to be improving and acalabrutinib was withheld, restart acalabrutinib with 1 level dose reduction or discontinue.
Grade 4^c Isolated ALT > 20 × ULN or Isolated Bilirubin > 10 × ULN	Discontinue AZD4573.	Discontinue acalabrutinib.
Grade 4 Isolated elevation ($\geq 20 \times$ ULN) in AST without concomitant elevation in ALT $\geq 20 \times$ ULN or concomitant elevation in TBL $\geq 2 \times$ ULN that fails to return to baseline level within 7 days from start of dosing	Discontinue AZD4573.	Discontinue acalabrutinib.
Grade 4^c Isolated AST elevation $\geq 20 \times$ ULN without concomitant elevation in ALT $\geq 20 \times$ ULN or TBL $\geq 2 \times$ ULN	1st occurrence If recovered to Grade ≤ 1 or baseline level within 7 days of the start of the infusion allow rechallenge at same dose level	Withhold or continue acalabrutinib (at Investigator discretion, after discussion with the Medical Monitor). To prevent disease progression, monitor disease parameters closely.
	2nd occurrence If recovered to Grade ≤ 1 or baseline level within 7 days of the start of the infusion allow rechallenge with 1 dose level reduction	Monitor ALT, AST, ALP, and bilirubin at least 1x per week. After 7 days if hepatic enzymes appear to be improving and

Event ^a	Action	
	AZD4573	Acalabrutinib
	3rd occurrence Discontinue AZD4573	acalabrutinib was withheld, restart acalabrutinib at current dose level at the 1st occurrence and with 1 level dose reduction at the 2nd occurrence . Discontinue acalabrutinib at the 3rd occurrence .
Concurrent elevations in ALT, AST, or bilirubin (Please also refer to Appendix E for actions to be taken in the event of PHL)		
ALT or AST $\geq 3 \times$ ULN with TBL $\geq 2 \times$ ULN (PHL) AND INR $\geq 1.5 \times$ ULN (or $\geq 1.5 \times$ baseline if elevated at baseline) of any duration	Discontinue AZD4573.	Discontinue acalabrutinib.
ALT or AST $\geq 3 \times$ ULN with the appearance of fatigue, nausea, vomiting, right upper quadrant pain or tenderness, fever, rash, and/or eosinophilia $> 5\%$	Discontinue AZD4573.	Discontinue acalabrutinib.
ALT or AST $\geq 3 \times$ ULN and TBL $\geq 2 \times$ ULN where TBL does not return to baseline level within 96 hours (-2/+12 hours) from start of dose and/or AST or ALT do not return to baseline level within 7 days from start of dose	Discontinue AZD4573.	Discontinue acalabrutinib.
Grade 3 elevation ($\geq 5 \times$ ULN) in ALT or AST with TBL elevation above baseline level or ULN, but $< 2 \times$ ULN that do not return to baseline level within 7 days	Discontinue AZD4573.	Discontinue acalabrutinib.
ALT and AST $\geq 3 \times$ ULN with concomitant TBL $\geq 2 \times$ ULN, NO increase in INR $\geq 1.5 \times$ ULN (or $1.5 \times$ baseline), and NO fatigue, nausea, vomiting, right upper quadrant pain or tenderness, fever, rash, and/or eosinophilia $> 5\%$	If recovered to Grade ≤ 1 or baseline level within 96 (-2/+12) hours, rechallenge at same dose level ^c	Withhold acalabrutinib until recovered. Once recovered, restart acalabrutinib at same dose.

^a Adverse reactions are graded using National Cancer Institute CTCAE version 5.0. All grades refer to CTCAE grading except for TLS, which uses the Howard modification of Cairo-Bishop criteria ([Howard et al 2011](#)).

- ^b Elevations in ALT or AST are considered isolated if bilirubin remains below Grade 1, and elevations in bilirubin are considered isolated if ALT and AST remain below Grade 1.
- ^c Participants who are considered for rechallenge in the event of Grade 4 transaminase increases or PHL must discuss possible risk of hepatotoxicity with the treating physician, who will document this discussion and participant agreement for continued treatment in the medical records.

Note: Adequate supportive therapy as per institutional guidelines should be given for all toxicities.

Abbreviations: ALP = alkaline phosphatase; ALT = alanine aminotransferase; AST = aspartate aminotransferase; CTCAE = Common Terminology Criteria for Adverse Events; INR = international normalised ratio; PHL = Potential Hy's Law; TBL = total bilirubin; ULN = upper limit of normal.

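### Module 2, Section 24.9: the text allows AZD4573 to restart at Grade 2 or lower where Table 31 requires Grade 1, and its flat 21-day limit with study withdrawal conflicts with Table 31 footnote b

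*Protocol*

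**What the plan says.** **Text of Section 24.9.** For a Grade 3 or 4 toxicity not attributable to the disease, dosing is interrupted and/or reduced. If the event comes down to CTCAE Grade 2 or lower "within 21 days and the participant was showing clinical benefit, treatment with study treatment(s) may be restarted". If it does not reach that level in 21 days, "then the participant should be withdrawn from the study and observed until resolution of the toxicity". The text adds: "Maximal drug interruption allowed for related toxicity for both AZD4573 and acalabrutinib is" 21 consecutive days or fewer, with no exception.

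**Table 31, Grade 3 or 4 non-haematological toxicities (liver excluded).**
- AZD4573, first occurrence: "Withhold dosing with AZD4573 until the toxicity has resolved to Grade 1, but no longer than 21 days", then resume at the same dose.
- AZD4573, later occurrences: a hold of up to 21 days, then "After resolution to Grade 1, reduce dose by one dose level when restarting AZD4573". The cell continues: "If no resolution within 21 days discontinue AZD4573".
- Acalabrutinib, both rows: "Withhold acalabrutinib until recovery to Grade" 2 or lower.
- Footnote b, attached to both AZD4573 rows: "In cases where more than 21 days are needed, a decision to continue, modify, or discontinue study treatment" is made case by case with the principal investigator and the Medical Monitor.

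**Related places.** Section 24.9.1, criterion 1, asks for recovery of treatment-related non-haematological toxicity to Grade 2 or lower before any restart. Section 24.10 lets a participant who stops one drug continue the other if benefiting. Before the restart text, Section 24.9 places the haematological and non-haematological guidance in Table 30 and the liver guidance in Table 31. They are in Tables 31 and 32.

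**The concern.** The same drug and the same event have two restart thresholds, and the looser one stands in the general text. A site working from the text could give AZD4573 again while a non-haematological toxicity is still Grade 2. After a first occurrence that would be at the unchanged dose, in a state in which the drug's own table row tells the site to keep holding.

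The second problem is what happens at 21 days. The text sets a hard limit and then takes the participant off the study. Footnote b allows treatment to continue or be modified past that point. Both cannot be followed. Read literally, study withdrawal would also close the route in Section 24.10 by which a participant in Period 2 stays on the remaining drug.

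Dose modifications and treatment discontinuation due to adverse events are components of both primary endpoints in Table 26, for monotherapy and for the combination. The same clinical course could be recorded as a restart at one site and as a continued hold or a discontinuation at another. With about 12 participants planned (Section 27.2), one such case would be visible in the summaries.

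**Working it through.** No figure is stated in the protocol to reproduce. The check is a side-by-side reading for Grade 3 or 4 non-haematological, non-liver events.

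| | Section 24.9 text | Table 31, AZD4573 | Table 31, acalabrutinib |
|---|---|---|---|
| Restart level, first occurrence | Grade 2 or lower | Grade 1 | Grade 2 or lower |
| Restart level, later occurrences | Grade 2 or lower | Grade 1 | Grade 2 or lower |
| Time limit | 21 days, no exception | 21 days, with footnote b | none stated in the cell |
| Not recovered at the limit | withdrawal from the study | later occurrences: discontinue AZD4573; both rows subject to footnote b | still withheld; at later occurrences, dose reduction or discontinuation |

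**Restart level.** The block has 2 drugs × 2 occurrence rows = 4 cells. The text's single threshold agrees with the 2 acalabrutinib cells and disagrees with the 2 AZD4573 cells, so it matches 2 of 4. In both mismatches it is looser by 2 − 1 = 1 grade.

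**Two courses worked through.**
1. *The event settles at Grade 2 within 21 days and the participant is benefiting.* Text: AZD4573 and acalabrutinib may both restart. Table: acalabrutinib may restart, but AZD4573 stays on hold until Grade 1.
2. *The event is still Grade 3 at day 21.* Text: the participant leaves the study. Table, later occurrence: AZD4573 is discontinued unless a footnote b decision says otherwise. Table, first occurrence: the hold may not exceed 21 days, again subject to footnote b. Acalabrutinib is still withheld in either case.

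**Where the 21-day conflict lies.** Both AZD4573 cells state 21 days themselves, so they agree with the text on the usual limit. Only footnote b departs from it. An unconditional maximum and a stated way past it are incompatible.

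**Whether Section 24.9.1 is a third conflicting rule.** It is not. Its criteria are conditions to be met before restarting, so Grade 2 or lower is a necessary minimum and a stricter table row can sit above it. But criteria 3 and 5 refer explicitly to Tables 32 and 31, while criterion 1 does not, so it gives no help in resolving the mismatch.

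**The case against.** The best defence is that the text is only a general introduction. Its paragraph opens with a generalising phrase, the restart wording is permissive, and it cites Table 31 for drug-specific modifications. Sections 26.1.10 and 26.1.10.7 also send sites to Table 31. A careful site would probably reach the stricter row. The wrong table numbers are a clerical slip, and the following paragraph cites Table 31 correctly.

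Much of this stands as mitigation, but it does not settle precedence. The generalising phrase introduces the sentence on Grade 1 and 2 events. The restart sentence sets out the conditions under which treatment may resume, and a reader can fairly take them as sufficient. The sentence on the 21-day maximum is not permissive at all. Table 31 is itself titled as recommendations, so a site could defend either course.

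Three stronger readings are tempting, and the protocol does not support them:
- *That Table 31 would at most stop AZD4573 where the text removes the participant from the study.* The text's withdrawal rule applies only above Grade 2. In that state Table 31 also withholds acalabrutinib and allows its discontinuation at later occurrences. In Period 1 AZD4573 is the only study drug, so stopping it ends study treatment.
- *That the protocol consistently separates stopping treatment from leaving the study, citing Section 26.1.10.9, which keeps participants with unresolved liver events on study for follow-up.* Section 24.2 says the opposite for potential Hy's Law with bilirubin still raised at 96 hours: the participant comes off the study while biochemistry is followed. The usage is not settled enough to carry that argument.
- *That a number of participants is affected.* The frequency of residual Grade 2 toxicity cannot be derived from the protocol, and nothing at hand shows that any Module 2 participant has been dosed.

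**Conclusion.** The inconsistency is real on two counts. First, the text permits AZD4573 to restart one grade earlier than Table 31 does, in both AZD4573 rows for non-haematological, non-liver events. Secondly, the unconditional 21-day maximum with study withdrawal contradicts footnote b and would defeat the single-drug continuation in Section 24.10.

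Importance is minor to moderate. It bears on dosing safety and on primary endpoint components. Against that, the module plans about 12 participants, tests no hypotheses, and belongs to a study whose enrolment has been permanently halted (Section 18.5). Section 23.6 lets participants who still benefit continue treatment after the primary analysis, so the instruction could still be used.

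Two assumptions apply. The core dose-modification section (6.12) and the core discontinuation and withdrawal sections (7.1, 7.2) lie in the part of the protocol not at hand; a precedence rule there would weaken the point. The Section 24.10 argument takes its continuation rule to apply during the study, although the section title refers to intervention after the study ends; its opening paragraph describes treatment until progression, which supports that reading.

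**What to change.** 1. In Section 24.9, state that Table 31 governs restart: after a Grade 3 or 4 non-haematological (non-liver) toxicity, AZD4573 restarts at Grade 1 and acalabrutinib at Grade 2 or lower.
2. Replace the study-withdrawal sentence and the flat 21-day maximum with discontinuation of the affected study drug(s) according to Table 31, including footnote b.
3. Keep Section 24.9.1 criterion 1 at Grade 2 or lower as a general minimum, and add: *and any stricter event-specific threshold in Table 31 is met*.
4. Correct the table numbers in Section 24.9: haematological and non-haematological guidance is in Table 31, and liver guidance is in Table 32.

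The cost is three sentences, one added clause and two table numbers. No new assessments or data are needed. The change requires the usual amendment approval and can go with the next amendment.
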